13.5 Times of Statistical Analyses29

14.0 Final Report and Publications29

15.0 References30

5.0 Introduction

Treatment of rheumatoid arthritis (RA) has advanced significantly after the introduction of biological agents and improved treatment recommendations. Current treatment guidelines for the management of RA advocate the use of an TNF-inhibitor in combination with MTX as first line biological therapy. Multiple studies have shown the synergistic effect of TNF-inhibitors and MTX. In February 2011, dosage regimens of methotrexate (MTX) were approved up to until ≤ 16 mg/week in Japan (2011 Japanese Guideline for MTX treatment with RA patient). Thus physicians may prescribe MTX in a maximum dose of ≤ 16 mg/week. Moreover MTX was also approved as first-line therapy in adult patients with RA.

MTX is a low-molecular-weight disease-modifying antirheumatic drug (DMARD) that has been demonstrated highly beneficial in inducing clinical remission, preventing the progression of bone destruction, improving quality of life (QOL), and ensuring durability and safety of treatment.¹⁻⁶⁾ On the basis of its usefulness in combination with other low-molecular-weight DMARDs and biologics, MTX is positioned as an anchor drug in the treatment of RA, and is one of the most commonly used low-molecular-weight DMARD in RA.⁷⁾ The benefits of MTX in combination with biological agents have been assessed in retrospective analyses of the data of post-marketing surveillance of biologics conducted prior to the approval of high-dose MTX treatment at ≥ 10 , ≤ 16 mg/week. Safety evaluation based on the incidence and patterns of adverse drug reactions (ADRs) by dose of MTX have revealed that the ADR profile does not differ significantly between lower and higher doses of MTX. Moreover, the efficacy of treatment appears better in patients receiving MTX at higher doses, which indicates a tendency toward dose-effect relationship. These results of retrospective analyses support the necessity of prospective studies to investigate the usefulness of treatment combining biological agents and high-dose MTX.

In the present prospective post-marketing observational study (PMOS), we will investigate the effectiveness and safety of treatment with adalimumab (Humira[®]) and high-dose MTX (≥ 12 mg/week).

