EULAR judgement criteria for response	
Both DAS28-4ESR and DAS28-4CRP should be evaluated in accordance with the following table.
 
  
 	EULAR DAS28 response	
 
 >1.2	0.6< ≤1.2	≤0.6	
   
 DAS28 at the evaluation time	≤3.2	Good response	Moderate response	No response	
 
 3.2< ≤5.1	Moderate response	Moderate response	No response	
 
 >5.1	Moderate response	No response	No response	
  
 
DAS28 response should be calculated from the EULAR DAS28 response (DAS28 of the origin) - (DAS28 at evaluation point). Good Response, Moderate Response, or No Response should be judged based on the DAS28 and the response at the evaluation time. Good Response and Moderate Response should be considered effective, and No Response as ineffective.
			EULAR DAS28 response			>1.2	0.6< ≤1.2	≤0.6	DAS28 at the evaluation time	≤3.2	Good response	Moderate response	No response	3.2< ≤5.1	Moderate response	Moderate response	No response	>5.1	Moderate response	No response	No response
				EULAR DAS28 response																		
		>1.2	0.6< ≤1.2	≤0.6																		
DAS28 at the evaluation time	≤3.2	Good response	Moderate response	No response																		
	3.2< ≤5.1	Moderate response	Moderate response	No response																		
	>5.1	Moderate response	No response	No response																		
SDAI	
It should be calculated by the following formula. $SDAI=(A)+(B)+(D)/10+(F)/10+(E)$ Refer to (A), (B) and (D) DAS28-4ESR (E) C-reactive protein (CRP) (mg/dL) (F) Global assessments of disease activity by the physician (VAS) (mm)
																					

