“Table 6.2.4 Summary of DAS28-4CRP by each Visit per Baseline MTX Dose”

Analysis object: Patients included in the efficacy analysis set (DAS28-4CRP)

Purpose of analysis: To indicate the number of patients by evaluation time, and summary statistics of the score and response for the DAS28-4CRP score by the group of MTX dose at the start of Humira treatment.

In addition, paired t tests should be performed for the response from the start of treatment, and the results of intergroup comparison by analysis of variance should be calculated by evaluation time.

Note: The group separation should follow the concomitant MTX dose (mg/week) in the patient background in “11. Data-layer separation.”

This form should be prepared only at the time of literature analysis.

“Table 6.2.5 Summary of DAS28-4CRP by each Visit per Average Usage MTX Dose of up to week 52”

Analysis object: Patients included in the efficacy analysis set (DAS28-4CRP)

Purpose of analysis: To indicate the number of patients by evaluation time, and summary statistics of the score and response for the DAS28-4CRP score by two groups of the mean MTX dose at week 52: < 12.0 mg/week group or ≥ 12.0 mg/week group. In addition, paired t tests should be performed for the response from baseline, and the results of intergroup comparison by analysis of variance should be calculated by evaluation time.

Note: It should be categorized by the following two categories based on the increase and decrease of the mean MTX dose from the start of Humira treatment to week 52: “< 12.0” and “12.0 \leq .”

This form should be prepared only at the time of literature analysis.

“Table 6.2.6 Univariate logistic analysis event: DAS28-4CRP ≤ 2.6 at week 104”

Analysis object: Patients included in the efficacy analysis set (DAS28-4CRP)

Purpose of analysis: To conduct univariate logistic regression analysis with the number of patients meeting the week 104 DAS28-4CRP < 2.6 as the objective variable and each patient background factor as the explanatory variable, and to indicate the number of patients analyzed, number of patients who developed ADRs, incidence rate, odds ratio, CI and p values.

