To handle the followings as the categorical data: [consultation category (outpatient, inpatient)], [gender (male, female)], [age category (< 15, ≥ 15 and < 30, ≥ 30 and < 50, ≥ 50 and < 65, and ≥ 65 and < 75, ≥ 75 and < 85, ≥ 85)], [age category: (< 15, ≥ 15 and < 65, ≥ 65)], [weight category (< 30, ≥ 30 and < 40, ≥ 40 and < 50, ≥ 50 and < 60, ≥ 60)], [category for duration of illness (< 3 months, ≥ 3 months and < 6 months, ≥ 6 months)], [complication (present, absent)], [smoking history (absent, present)], [RA stage/progression (Stage I/Stage II, Stage III/Stage IV)], [RA disability level (Class I/Class II, Class III/Class IV)], [past history (absent, present)], [history of allergy (absent, present)], [MTX at treatment start (≥ 12.0 mg/week and < 14.0mg/week, ≥ 14.0 mg/week and < 16.0mg/week, ≥ 16.0 mg/week)], [DMARDs at treatment start (excluding MTX) (absent, present)], [adrenocortical hormones at treatment start (absent, present)], [DMARDs during treatment (absent, present)], [adrenocortical hormones during treatment (absent, present)], [other concomitant drugs during treatment (absent, present)], [DAS28-4CRP at treatment start (< 2.6, 2.6 \leq)]; and also indicate the results for [age], [weight], [duration of illness] and [DAS28-4CRP at treatment start] as the quantitative data.

Note: This form should be prepared only at the time of literature analysis.

“Table 6.2.7.1 DAS28-4CRP Score of Week 24 and Mean Usage MTX dose Change from Week 24 to Week 52”

Analysis object: Patients included in the efficacy analysis set (DAS28-4CRP)

Purpose of analysis: Regarding the frequency of DAS28-4CRP Remission (< 2.6) at week 24, indicate from week 24 to week 52 by MTX dose reduction and compare them between the factors by χ^2 test.

Furthermore, a scatter graph with the DAS28-4CRP score at week 12 by patient as the Y axis and the change in MTX dose from week 24 to week 52 as the X axis should also be illustrated.

Note: The following tables should also be created with the same layout .

“Table 6.2.7.2 DAS28-4CRP Score of Week 24 and Mean Usage MTX dose Change from Week 24 to Week 104”

Note: The change in MTX dose from week 24 to week 104 should be compared in this form.

“Table 6.2.7.3 DAS28-4CRP Score of Week 12 and Mean Usage MTX dose Change from Week 12 to Week 52”

Note: The change in MTX dose from week 12 to week 52 and DAS28-4CRP Remission (< 2.6) at week 12 should be compared in this form.

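### Every SAP comparison of DAS28-4CRP by MTX dose is unadjusted for baseline DAS28-4CRP, which costs precision and lets a baseline gap between dose groups appear as, or mask, a dose difference

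*SAP*

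**What the plan says.** SAP section 13.3, Table 6.2.4, splits patients by MTX dose at the start of adalimumab: "The group separation should follow the concomitant MTX dose (mg/week) in the patient background". Section 11 gives three groups: 12 to under 14, 14 to under 16, and 16 mg/week or more. The instruction, applied at each evaluation time, is "paired t tests should be performed for the response from the start of treatment, and the results of intergroup comparison by analysis of variance". No covariate is named. Response is a change score, defined in SAP section 10.3 as baseline minus visit value: "DAS28 of the origin) - (DAS28 at evaluation point".

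Other SAP tables that relate DAS28-4CRP to MTX dose:

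- Table 6.2.2 groups by change in MTX dose up to week 52 and states that response is compared by ANOVA. Table 6.2.5 groups by mean MTX dose up to week 52 and also uses ANOVA.
- Table 6.2.6 is to "conduct univariate logistic regression analysis with the number of patients meeting the week 104 DAS28-4CRP < 2.6 as the objective variable". The factor "MTX at treatment start" is one of those entered singly. Baseline disease activity is a separate single factor, including "DAS28-4CRP at treatment start] as the quantitative data".
- Table 6.8.1 gives EULAR DAS28-4CRP response at final evaluation by the section 11 background factors, which include MTX dose. The note to Table 6.8.4.X shows that these carry chi-square tests.
- Tables 6.2.7.1 to 6.2.7.4 run the other way, relating remission at week 12 or 24 to later MTX dose change. They are also unadjusted.

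The only multivariable models, Tables 6.9.6.1 and 6.9.6.2, are for mTSS. They contain gender, complication, stage and duration of illness, but neither MTX dose nor baseline DAS28.

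**The concern.** The study is non-interventional (protocol section 7.6.1), so the physician chooses the MTX dose and nothing balances baseline disease activity across dose groups. Patients who start with a higher DAS28 usually show a larger fall. An ANOVA of the fall therefore mixes any baseline difference with any dose difference and cannot separate them. Even when group baselines are equal, the change score carries baseline variation that a covariate would remove.

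A published p value by MTX dose invites interpretation, because the protocol Introduction cites earlier retrospective data, "which indicates a tendency toward dose-effect relationship". The protocol synopsis also announces regression analysis of factors that influence effectiveness. For DAS28-4CRP the SAP provides only one-factor tests.

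The missing covariate is already collected: DAS28-CRP above 3.2 is an inclusion criterion, so every eligible patient has a baseline value.

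**Working it through.** **The plan's own figure.** The SAP gives no power or precision for the MTX comparison. Its only sample-size figure is for week 52 remission, 55% against 42.7%, two-sided 0.05, 90% power:

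n = [1.960 × √(0.427 × 0.573) + 1.282 × √(0.55 × 0.45)]² / 0.123² = 170.7, rounded up to 171; 171 / (1 − 0.5) = 342, set at 350.

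This reproduces. It is used below only as the likely number of evaluable patients at week 52, about 57 per group if split equally (171 / 3).

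**Inputs.** SDs, baseline-to-follow-up correlation r, group sizes and baseline gaps are not in the documents. Assumed: baseline SD s0 = 1.0, follow-up SD s1 = 1.1, r from 0.2 to 0.7.

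**Formulas.**
- Variance of change: s0² + s1² − 2·r·s0·s1
- ANCOVA residual variance: s1²·(1 − r²)
- Shift in mean response per unit of baseline gap, with no dose effect at a given baseline: 1 − r·s1/s0

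| r | Var(change) | Var(ANCOVA) | Ratio | Share of patients lost (1 − 1/ratio) | Shift for a 0.3 gap |
|---|---|---|---|---|---|
| 0.2 | 2.21 − 0.44 = 1.77 | 1.21 × 0.96 = 1.162 | 1.52 | 34% | 0.3 × 0.78 = 0.23 |
| 0.35 | 2.21 − 0.77 = 1.44 | 1.21 × 0.8775 = 1.062 | 1.36 | 26% | 0.3 × 0.615 = 0.18 |
| 0.5 | 2.21 − 1.10 = 1.11 | 1.21 × 0.75 = 0.908 | 1.22 | 18% | 0.3 × 0.45 = 0.14 |
| 0.7 | 2.21 − 1.54 = 0.67 | 1.21 × 0.51 = 0.617 | 1.09 | 8% | 0.3 × 0.23 = 0.07 |

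**Check with equal SDs.** The ratio of ANCOVA to change variance becomes (1 + r)/2: 0.60 at r = 0.2 and 0.85 at r = 0.7. By that measure 171 patients analysed as change are worth about 103 to 146 analysed by ANCOVA.

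**False positives.** Simulation: 4,000 runs per setting, N = 171, both SDs 1, r = 0.3 or 0.5, groups of 57/57/57 or 100/40/31, no dose effect at a given baseline.

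| Baseline gap, lowest to highest group | ANOVA of change rejects | ANCOVA rejects |
|---|---|---|
| 0 | 4–5% | 4–5% |
| 0.3 | 9–13% | about 5% |
| 0.5 | 19–27% | about 5% |

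The null here is no dose effect given baseline, which is the question ANCOVA answers. Its 5% rate therefore follows from how the data were generated and does not show that ANCOVA is unbiased in general.

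**The case against.** A reader might infer two stronger things. The first is that Table 6.2.4 is the only test of DAS28-4CRP by baseline MTX dose. It is not: Tables 6.2.6 and 6.8.1 also test it, on binary outcomes. The second is that baseline differences will be taken for MTX dose effects. No section says the ANOVA will be read that way, and the bias needs a baseline gap that the documents do not show. A gap would also be visible, because Table 6.2.4 summarises scores as well as responses and Tables 7.1.2 and 7.1.3 describe baseline data by MTX group. Seeing an imbalance does not correct the comparison, however, and the precision loss needs no gap.

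The stakes are limited. Tables 6.2.2, 6.2.4, 6.2.5 and 6.2.6 are prepared only for the literature analysis. The protocol objectives contain no comparison of doses within the enrolled range, and the dose-effect remark in the Introduction concerns lower against higher MTX doses in retrospective data. This stands, and it keeps the point secondary.

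The remedy has limits too. In non-randomised groups, change-score analysis and ANCOVA answer different questions and can disagree when baselines differ. Baseline DAS28 is measured after at least 3 months on MTX and may already reflect its dose. Stage, corticosteroids, other DMARDs and duration of illness would remain unadjusted. In Tables 6.2.2 and 6.2.5 the groups are formed during follow-up, which a baseline covariate does not address. These objections stand, so the adjusted result belongs beside the unadjusted one and should not be presented as causal.

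A 1-df linear trend test is sometimes urged as well. Where it has 80% power, the 2-df test has 71% if the effect is truly linear, but the 2-df test can also detect a plateau. The trend test is optional.

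**Conclusion.** The point holds as a secondary one. No SAP comparison of DAS28-4CRP by MTX dose takes baseline DAS28-4CRP into account. Under the assumed SDs, the cost in precision is equivalent to about 34% of patients at a correlation of 0.2 and about 8% at 0.7. A spurious or masked dose difference is possible but not established: it would be about 0.23 to 0.07 DAS28 units for a 0.3-point baseline gap, and zero without a gap. All these sizes rest on assumptions and should be quoted as ranges.

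The documents support saying that a baseline difference could be mistaken for a dose difference. They do not support saying that it will be, or that the study's main conclusion is at risk. The week 52 remission endpoint and the 171 and 350 figures do not depend on these tables.

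**What to change.** In Table 6.2.4, and likewise in Tables 6.2.2 and 6.2.5, make the between-group comparison an ANCOVA of DAS28-4CRP at each visit, with MTX group as factor and baseline DAS28-4CRP as covariate. Report adjusted group means and their differences with 95% CIs. Keep the unadjusted summaries and the ANOVA alongside. State in the table note that the comparison is exploratory, that MTX dose was not randomised, and that the result is not a causal dose effect.

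The cost is SAP wording and one more model per table, with no new data. The downside is an estimand conditional on a baseline measured while patients were already taking MTX, which the note should say.

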4.3. Planned sample size

(1) Planned number of patients surveyed

350 patients

(2) Rationale for setting

The patient with Disease Activity Score 28 (hereafter, referred to as “DAS28”) below 2.6 at week 52 was estimated to be 55% (the expected observation was 55% and the estimated difference was 12.3% for the literature data 42.7%), and the number of patients required to detect at a 5% level of significance level (paired) and a 90% power was calculated to be 171 patients. As the number needed to treat to secure this number of patients, the dropout rate at week 52 in this survey was assumed to be 50% based on the dropout rate of approximately 32% at week 24 in the all-case surveillance with Humira, and the planned number of patients surveyed was calculated to be 350 patients.

5. Items to be evaluated in analysis and examining method

(1) Analysis items

1) Matters concerning patient composition

- 1) Number of patients with returned CRFs
- 2) Number of patients included in the safety analysis set
- 3) Number of patients included in the efficacy analysis set

- 2) Matters concerning safety
 - 1) List of incidences of ADRs/infections
 - 2) Factors considered to have an influence on safety
Incidence of ADRs by patient background factor, etc.
 - 3) AEs occurred during or after treatment
List of incidences of serious AEs, etc.
 - 3) Matters concerning efficacy
 - 1) DAS28 response, trend, percentage of remission, etc.
 - 2) CDAI response, trend, percentage of remission, etc.
 - 3) SDAI response, trend, percentage of remission, etc.
 - 4) Trends in HAQ, etc.
 - 5) Trends in EQ-5D, etc.
 - 6) Trends in mTSS/bone erosion score/joint space narrowing score and the percentage of patients without worsening of mTSS/bone erosion score/joint space narrowing score (change from the survey start < 0 and < 0.5), etc.
 - 7) Factors considered to have an influence on efficacy (list of efficacy by patient background factor, etc.)
- (2) Analysis methods
Appropriate methods including χ^2 test according to the scale and nature of the analysis data should be used.

6. Schedule of the analysis

Purpose of the analysis	Survey unit period and time frame for reexamination
The 11th Periodic Safety Report	December 31, 2012 - June 30, 2013
The 12th Periodic Safety Report	July 1, 2013 - December 31, 2013
The 13th Periodic Safety Report	January 1, 2014 - June 30, 2014
The 14th Periodic Safety Report	July 1, 2014 - December 31, 2014

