9.6. Level of significance

In principle, the significance level of statistical analysis used in this survey is two-sided 5%. $p < 0.05$ ($< 5\%$) should be considered significant.

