Presence of complication: others	Patients with the complication items applicable to the details of blood disorders [diabetes mellitus, gastrointestinal disorder, osteoporosis, malignant tumour, demyelinating disorders, collagen disorders (other than rheumatoid arthritis), others] should be handles as “present,” when there is no description in the presence of complications, it should be handled as “undescribed,” respectively, and others should be handled as “absent.”
Presence of a past history	When any of the details of the past history is evaluated as present, it should be handled as “present,” when it is described as no complication, it should be handled as “absent,” and when there is no description both in past history and the details, it should be handled as “undescribed.”

Name of data	Derivation and calculation methods
Presence of a history of allergy	If there is nothing applicable to a history of allergy, it should be handled as “undescribed.” In the details, if the patient is applicable to both “drugs” and “food,” it should be handled as “both.”
RA stage/progression	If there is no description in the RA stage/progression, it should be handles as “undescribed.”
Disabilities in RA	If there is no description in the RA disability index, it should be handles as “undescribed.”
Presence of concomitant drugs (At start date of Humira treatment)	If there is any drug administration on the date of initial Humira treatment, it should be handled as “present,” and others should be handled as “absent.”
Presence of concomitant drugs (During treatment with Humira)	If there is any drug administration during treatment with Humira, it should be handled as “present,” and others should be handled as “absent.” Administration during treatment with Humira refers to all administration cases not applicable to the followings. 
 • The completion date of treatment with a concomitant drug is prior to the date of initial Humira treatment • The start date of treatment with a concomitant drug is after the date of final Humira treatment
Concomitant drug: MTX (mg/week)	The dose of MTX during the period including the date of initial Humira treatment should be sorted into the following three categories: “ ≥ 12.0 mg/week and < 14.0 mg/week,” “ ≥ 14.0 mg/week and < 16.0 mg/week,” and “ ≥ 16.0 mg/week.”

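### SAP Table 6.2.4 compares DAS28-4CRP response across three ordered baseline MTX bands without using their order, and no DAS28-4CRP model takes baseline MTX dose as a number

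*SAP*

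**What the plan says.** **The comparison.** SAP 13.3, Table 6.2.4, summarises DAS28-4CRP score and response by baseline MTX band at each visit. For the test it says: "paired t tests should be performed for the response from the start of treatment, and the results of intergroup comparison by analysis of variance". On grouping: "The group separation should follow the concomitant MTX dose (mg/week) in the patient background". SAP 10.1 says the dose at the first Humira date "should be sorted into the following three categories", namely 12 to <14, 14 to <16 and ≥16 mg/week, and SAP 11 repeats these bands. The table is produced only for the literature analysis. SAP 9.6 sets a two-sided 5% level.

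**Other DAS28-4CRP analyses that use MTX.**
- Table 6.2.6 (logistic model, week-104 remission) enters baseline MTX as the same three categories. After the list of categorical factors it adds: "also indicate the results for [age], [weight], [duration of illness] and [DAS28-4CRP at treatment start] as the quantitative data". MTX is not in that list.
- Table 6.8.1 gives EULAR response by background factor, MTX bands included. The note to Table 6.8.4.X shows that its test is χ².
- Tables 6.2.2 and 6.2.5 group patients by change in MTX dose or by mean dose and use analysis of variance.
- Tables 6.2.7.1 to 6.2.7.4 plot DAS28-4CRP score against change in MTX dose and run χ² tests on dose reduction. Table 7.1 gives summary statistics of MTX dose.

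**Where order is used.** Tables 6.9.4.1 and 6.9.4.2 apply Spearman correlation to background items that include the MTX bands, but the outcome is mTSS.

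**Background.** Protocol 5.0 says of earlier retrospective data that efficacy appeared better at higher MTX doses, "which indicates a tendency toward dose-effect relationship".

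**The concern.** The bands come from a numeric dose that runs from 12 mg/week to the approved maximum of 16 (Protocol 5.0). A one-way ANOVA on three groups gives the same p value however the bands are ordered. Half of its degrees of freedom go to departures from a straight line, and it yields no estimate of change in response per mg/week. A modest steady gradient is therefore more likely to be published as no difference between dose groups, with no interval to show what gradient the data allow. The SAP already runs four other baseline factors as numbers in Table 6.2.6, so leaving MTX out looks like an oversight.

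**Working it through.** **1. The plan's own figure.** SAP 4.3 says of the primary remission endpoint: "a 90% power was calculated to be 171 patients". With p0 = 0.427, p1 = 0.55, two-sided 5% and 90% power:

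n = [1.960·√(0.427·0.573) + 1.282·√(0.55·0.45)]² / 0.123² = (0.9695 + 0.6376)² / 0.01513 = 170.7, so 171.

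With 50% dropout, 171/0.5 = 342, set at 350. The figure reproduces. It belongs to a one-sample test of remission; neither document states power for Table 6.2.4. N = 171 is used below only as a plausible evaluable number.

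**2. Assumptions.** Effect per band, SD of response and patients per band are not given. Bands are scored as equally spaced (12, 14, 16).

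**3. Power formulas.** Let λ = N·Var(band means)/σ².
- ANOVA: P[F(2, 168; λ) > 3.050].
- Linear trend: P[F(1, 169; λ·r²) > 3.897], where r² is the share of between-band variance on a straight line. For an exactly linear pattern r² = 1 and both tests have the same λ, whatever the split between bands.

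**4. Linear effect, N = 171.**

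| λ | Trend power | ANOVA power | Loss (points) |
|---|---|---|---|
| 0.43 | 10% | 8.3% | 1.7 |
| 1.26 | 20% | 15.4% | 4.6 |
| 3.89 | 50% | 39.9% | 10.1 |
| 4.95 | 60% | 49.2% | 10.8 |
| 6.24 | 70% | 59.4% | 10.6 |
| 7.94 | 80% | 70.6% | 9.4 |
| 10.63 | 90% | 83.3% | 6.7 |

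At N = 350 the 80% row becomes 70.7%. For 80% power the ANOVA needs about 24% more patients (ratio of λ = 1.235).

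To place these rows: with equal bands, 80% trend power needs a slope of √(7.939/(171·0.667)) = 0.26 SD per band. At 0.10 SD per band the trend test has 19% and the ANOVA 14%.

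**5. Other shapes, holding λ = 7.94 (ANOVA 70.6%).**
- *Middle band at 25% or 75% of the full effect:* trend 76-79% over the seven splits tried, 6-8 points better.
- *Step (0,1,1 or 0,0,1):* with equal bands r² = (1/3)²/(2/3 · 2/9) = 0.75 and trend power is 68.0%, 2.6 points worse. For the splits 50/25/25, 50/20/30, 60/20/20 and 40/20/40 it is 68-73%, within 3 points either way. The extremes are 61.5% (70/20/10, step at the top band) and 76.1% (60/10/30, step at the middle band).
- *Umbrella (0,1,0.5):* with equal bands r² = (1/6)²/(2/3 · 1/6) = 0.25 and trend power is 28.8%. For 50/25/25 and 50/20/30 it is 43-44%.

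**The case against.** **The study does not ask this question.** The objectives (Protocol 2.0 and 7.0) and the SAP's survey purpose (4.1) concern effectiveness and safety with MTX at ≥12 mg/week in one arm. None asks about a gradient from 12 to 16. The retrospective data in Protocol 5.0, the ≥10 mg/week finding in 6.0 and Table 3 in 13.1 (8.5 ± 2.9 against ≥12) all set lower doses against higher ones. They explain why patients at ≥12 were chosen. This stands: a reader might infer that the plan mishandles the study's central question, and the documents do not support that.

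**MTX in mg/week is not ignored.** A reader might infer from the banding that dose is never analysed on its own scale. Table 7.1 and the 6.2.7.x plots use it, and the mTSS Spearman tables use band order. This also stands. The gap is narrower: no DAS28-4CRP test or model takes baseline dose as a quantitative explanatory variable.

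**Direction is visible.** Table 6.2.4 prints summaries for each band, so a reader can see which way the means run. That answers part of the concern, but supplies neither a slope nor an interval.

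**The trend test can lose, and dose is not randomised.** The physician chooses the dose (Protocol 7.6.1), so a non-monotone pattern cannot be excluded. An unadjusted slope is open to confounding by indication, and a slope at every visit adds tests. These points stand. They argue against replacing the ANOVA or calling the slope the definitive dose test, but not against reporting it beside the ANOVA.

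**Conclusion.** The point holds as a cheap improvement to an exploratory table. For DAS28-4CRP, baseline MTX is handled only as unordered bands: by ANOVA for mean response, logistic categories for remission and χ² for EULAR response.

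The loss is about 7-11 points if the effect is linear and a trend test would have 60-90% power; 80% against 71% is one case. It is 2-5 points at 10-20% trend power, near nil for most step shapes (from 9 points worse to 5-6 better at the extremes tried), and strongly reversed for an umbrella shape. An unconditional loss of 9 points cannot be read from the documents.

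The ANOVA is a valid test and Table 6.2.4 has no stated power to miss. Nothing here touches the week-52 remission endpoint, the 171 evaluable patients or the target of 350.

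**What to change.** 1. In Table 6.2.4, keep the ANOVA and the band summaries. Add beside them a prespecified linear model of DAS28-4CRP response on baseline MTX dose in mg/week (1 df), reporting the slope per 2 mg/week with 95% CI and p value. Name week 52, the primary endpoint's time point, as the key time point and treat other visits as supportive.
2. In Tables 6.2.6, 6.9.5.1 and 6.9.5.2, add MTX dose at treatment start to the factors also shown as quantitative data. For the mTSS tables this is for consistency; no power gain was calculated there.
3. Label these results exploratory and associational, because the dose is the physician's choice.

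The cost is a sentence of SAP wording and one model line per table, using data already collected. The downside is one more unadjusted exploratory test, with weak power against non-monotone patterns, which the retained ANOVA covers.
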